The study will last a duration of about an hour, and take place on a single day. It will be conducted in a lab room of the PI, which is isolated from others in the space. We will recruit 30 participants. We hope to recruit people who show no tension in the upper back, others with moderate tension, and yet others tension to a greater degree. We will assign participants to a group based on the screening question, administered via Qualtrics, which will be asked of them upon their response to our email advertisement. We are attempting to screen so as to attain a balance in number of participants between the groups. Once a participant is selected to participate, we will invite them and have them sign the consent form. After this, they will complete a demographic questionnaire, administered verbally. Then, they will change into the clothing (e.g., sports bra, halter top, or swimming suit, etc.) that they were asked to bring in order to expose their upper back/neck region. This will take place in a separate, isolated room within the laboratory space, and we will provide them also with a gown for added privacy. Two researchers will be in the room during the session, with the gender of the researchers taken into account per participant. For example, for a male participant, we plan to have a male researcher present during the session along with the female physical therapist. For a female participant, we plan to have both the female physical therapist and a female researcher present. Next, the actual study procedures include that the proctors will apply a non-toxic, washable ink to the skin of the participant's upper back, in a square about 10 by 10 centimeters. This is easily washed off at the study's conclusion. Once the ink is applied, we will ask the participant to lie down on a massage table. An experienced, trained, and licensed physical therapist will perform an assessment manually, where they will compress their fingers into the skin, as well as

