Title: Optical Measurements of the Skin Surface to Infer Distinctions in Myofascial Tissue Stiffness

NCT number: NCT06390085

Date: February 3rd, 2023

Statistical Design and Power

Aim 1. We will evaluate the sensitivity of a suite of mechanical biomarkers. Using the imaging approach, we will create an optimal set of biomarkers which is the best classifier of myofascial pain state. In order to select the best suite of complementary metrics, which are most effective in predicting pain state, and which are simplest to accurate we will develop a classification strategy, we will perform multi-dimensional cluster analysis based on measured biomarkers. By using the biomarkers as predictors, data points representing different stimulus sets will be clustered into certain distinct groups based on the minimized average deviation (Jenks natural breaks classification method, 1-dimensional) and the minimized distance to the centroid (k-Means clustering, 2,3-dimensional). The match rate between clustered groups and ground-truth stimulus sets will determine the utility of unique biomarkers.

Aim 2. We will refine the requirements of the imaging deployment by evaluating tradeoffs in the array of ink speckles on the skin, in particular their density and heterogeneity requirements, to determine to what extent the density can be reduced yet still achieve similar imaging accuracy. We will perform ANOVA and t-tests with p values set at 0.5.

Sample size justification and power. Aim 1 will enroll 15 individuals. We will have a >80% power to identify biomarkers that have a moderate/strong rank correlation (e.g., Spearman's correlation ≥ 0.57) with pain. Aim 2 will enroll 6 individuals. These participants will be evaluated in refining requirements for imaging deployment, data collection, and data analysis.

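### Aim 2 asks whether sparser speckles give similar accuracy but plans difference tests in 6 people with no acceptable-loss margin; paired re-analysis of the Aim 1 recordings would answer it better

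*SAP*

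**What the plan says.** In the SAP (Statistical Design and Power, Aim 2) the purpose is "to determine to what extent the density can be reduced yet still achieve similar imaging accuracy". The features of the speckle array under study are "in particular their density and heterogeneity requirements". The whole analysis is one sentence: "We will perform ANOVA and t-tests with p values set at 0.5".

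The sample size paragraph gives "Aim 1 will enroll 15 individuals" and "Aim 2 will enroll 6 individuals". The only reason given for the 6 is "These participants will be evaluated in refining requirements for imaging deployment, data collection, and data analysis". There is no power, effect size, SD, margin, accuracy measure, reference standard or number of density levels. The SAP does not say whether the tests are paired, whether density is varied in ink or by computer, or whether the 6 are separate from the 15.

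The protocol's study overview describes ink applied to the upper back "in a square about 10 by 10 centimeters". Both sides are then assessed on video, before and after the massage. Under Data Sources (Imaging data) it describes three-camera video. It does not mention Aim 2, density conditions or software thinning.

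**The concern.** Asking whether accuracy stays similar is an equivalence question: the data must rule out a loss large enough to matter. ANOVA and t-tests address whether a difference can be detected. With few people a real loss easily goes undetected, and with no margin the only available route to calling two densities similar is a non-significant test.

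At stake is the speckle density carried into later work, since the protocol presents the study as preparation for a grant application. If density is cut on the strength of a null result in 6 people, the system could lose accuracy unnoticed. The Aim 1 sessions already produce video of an inked field. A reduced pattern made from such a recording can be compared with its own parent, which removes differences in person, tissue and applied force from the contrast.

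**Working it through.** **Plan's own figure.** The Aim 2 size of 6 has no stated inputs, so there is nothing to reproduce.

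**Inputs from the documents.** n = 6 for Aim 2 and n = 15 for Aim 1 (SAP, sample size paragraph).

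**Assumptions.**
- Two-sided alpha 0.05. At the printed 0.5, a density with no true difference would be declared different half the time.
- Results are in SDs of the within-person difference (reduced minus full density), because no SD is given. That SD is taken to be the same at both sample sizes.
- Equivalence margins of 0.5, 0.75 and 1 SD. The documents give none, so a range is shown.
- One summary difference per person. Side and pre/post recordings are not counted as extra people.

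**Step 1: precision, all people paired.** Half-width = t(0.975, n−1)/√n.
- n = 6: 2.571/√6 = 1.05 SD
- n = 15: 2.145/√15 = 0.55 SD
- Ratio: 1.049/0.554 = 1.9

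**Step 2: chance of missing a real loss.** For a true loss of 1 SD of the paired difference, the paired t-test has noncentrality 1 × √n.
- n = 6: non-significant about 49% of the time
- n = 15: non-significant about 5% of the time

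**Step 3: chance of showing equivalence when densities truly do not differ.** Two one-sided paired t-tests at 5% each, by simulation. Equivalence is declared when mean ± t(0.95, n−1) × s/√n lies wholly inside the margin.

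| Assumed margin | n = 6 | n = 15 |
|---|---|---|
| 0.5 SD | 2% | 20% |
| 0.75 SD | 15% | 74% |
| 1 SD | 41% | 96% |

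Even with full pairing, 6 people are unlikely to demonstrate equivalence at any of these margins. Fifteen do well at 1 SD, moderately at 0.75 SD and poorly at 0.5 SD.

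**The case against.** **Between-person design.** A reader might infer that density can only differ between people, because the protocol describes one inked square and no density conditions. The 6 would then be split, say 3 versus 3, with a half-width of t(0.975, 4) × √(2/3) = 2.27 between-person SDs. The documents do not support this. They are silent on the design, and one ink application is compatible with software thinning within a person. The protocol does not say that the pattern is fixed either. The 2.27 is also in different units from the paired figures, so the two should not be read as one series.

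**Size of the gain.** A reader might also infer a very large gain in precision. If the 6 are already compared within person, the gain is 1.9-fold and comes only from the larger n. Figures for 30 people would rest on the protocol overview. That number conflicts with the protocol's own group fields (3 × 15 = 45) and is not the SAP's Aim 1 size.

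**Limits of thinning.** Masking measures agreement with the full pattern, not accuracy against an independent reference. It cannot test denser patterns and only partly tests heterogeneity. This objection stands and limits what the remedy can claim.

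**Purpose of Aim 2.** It is engineering refinement with no power claim, and the SAP does not say outright that a null test will be read as similarity. That tempers the severity. However, the plan names a similarity question and provides no other way to answer it, so the mismatch between question and method remains.

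**Conclusion.** The point holds as a mismatch between question and method. With no acceptable-loss margin, difference tests in 6 people cannot support a conclusion that accuracy is similar, even if every comparison is paired. The size rests on the assumed alpha of 0.05, the assumed margins and a common SD of the paired difference. If the acceptable loss is as small as 0.5 SD, 15 people are also too few. Whether the remedy saves participants is unknown, because the SAP does not say whether the 6 are additional to the 15.

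**What to change.** In the SAP, Aim 2:
- State that reduced-density versions are made by masking speckles in all Aim 1 recordings, and that each is compared with its own full-density result.
- Define the accuracy measure, the density levels and the largest acceptable loss before analysis.
- Report paired differences with 95% intervals against that loss, treating side and pre/post recordings as repeated measures within a person.
- Correct or explain the 0.5 threshold.
- Use the 6 Aim 2 participants as a descriptive check of the chosen density with physically sparser ink, and say whether they are separate from the 15.
- State that masking assesses agreement with the full pattern, does not cover denser patterns and covers heterogeneity only in part.

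Reconcile the sample sizes (SAP 15 and 6; protocol 30 in the overview, 45 from the group fields) so that the number of recordings is known. The cost is image-processing time and a few sentences of SAP text. No participants beyond those planned are needed.
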